5.3.3 Overall benefit-risk and ethical assessment

In the advanced NSCLC post-EGFR TKI treatment failure setting that has been chosen for initial study with AZD9291, prolonged survival rates are very low (~16 months for second line therapy,

~10 months for third line therapy) and there is a huge unmet clinical need for novel therapeutic agents for patients who have developed the resistance mutation. There are no established well proven therapeutic options for this specific T790M+ NSCLC patient population. Although there can be no certainty of clinical benefit to patients, the biological hypothesis, non-clinical and preliminary clinical efficacy data with AZD9291 support the notion that dual EGFR mutation inhibition may be a valid target for the treatment of NSCLC tumours driven via this pathway and may, in addition, delay the development of resistance via T790M in the first line therapy naive population.

The selected starting dose for this study is within the range that is predicted to provide biological activity based upon non-clinical explant models, in accordance with the ICH S9 Nonclinical Evaluation for Anticancer Pharmaceuticals Section III.A principle of selecting a dose 'that is expected to have pharmacologic effects'. The preliminary efficacy data from this study (see Investigator Brochure) showed that objective responses occurred at the starting dose. The toxicological profile of AZD9291 has been evaluated in rats and dogs in studies of up to one month in duration. In accordance with ICH S9 Nonclinical Evaluation for Anticancer Pharmaceuticals which states in Section III.C that 'In Phase 1 clinical trials, treatment can continue according to the patient's response' (ICH S9), dosing of AZD9291 will extend beyond one month if there is some evidence of therapeutic benefit (ie, lack of disease progression with an acceptable tolerability profile). The non-clinical safety profile has not identified any risks that would preclude investigation in this setting. The study design aims to minimise potential risks, and monitoring is in place for those risks deemed to be most likely or serious.

The investigation of AZD9291 in this patient population appears acceptable, based upon the nonclinical safety profile, preliminary signals for clinical efficacy, and the lack of effective alternative treatments available to patients, the limited life expectancy due to malignant disease, and the strength of the scientific hypothesis under evaluation. Thus the benefit/risk assessment for this first-into-man Phase I study support the oral administration of AZD9291 to patients with advanced NSCLC in the post-EGFR TKI treatment failure and treatment-naive settings, according to the proposed study design.

5.4 Discontinuation of investigational product and withdrawal from study

Patients may be discontinued from investigational product in the following situations:

- Patient decision. The patient is at any time free to withdraw his/her participation in the study, without prejudice
- Adverse events
- Pregnancy
- Severe non-compliance to this protocol as judged by the investigator and/or AstraZeneca

- Confirmed disease progression
- Patients incorrectly initated on investigational product (Section 5.4.2)

Patients that are withdrawn from the study but are evaluable will not be replaced. Any patient that is withdrawn and is not evaluable will be replaced to ensure a minimum number of evaluable patients.

Patients may withdraw from any aspects of the voluntary exploratory research (see Section 6.9.5) at any time, without prejudice to further treatment and independent of any decision concerning participation in other aspects of the main study. Procedures for withdrawal from the exploratory research are outlined in Section 6.9.5

5.4.1 Procedures for discontinuation of a patient from investigational product

Once study medication is permanently discontinued it cannot be restarted.

A patient who discontinues study treatment is not always automatically withdrawn from the study. If a patient is withdrawn from study, see Section 5.4.3

Any patients who discontinue study treatment for reasons other than objective disease progression should have tumour assessments scans performed as scheduled in the protocol (see Table 2, Table 3 and Table 4 until objective disease progression is documented or death occurs, unless consent is withdrawn. Study procedure related SAEs and concomitant medication must be captured until the patient no longer has RECIST 1.1 assessments (disease progression or permanent withdrawal from the study).

5.4.2 Procedures for handling patients incorrectly initiated on investigational product

Patients who fail to meet the inclusion/exclusion criteria should not, under any circumstances, be enrolled or receive study medication. There can be no exceptions to this rule.

Where patients that do not meet the inclusion criteria are enrolled in error or incorrectly started on treatment, or where patients subsequently fail to meet the study criteria post initiation, the investigator should inform the AstraZeneca Global Study Team Physician immediately. The decision on when to discontinue the ineligible patient from the study is based on the medical/ safety risk for the patient. The AstraZeneca Global Study Team Physician is to ensure all such contacts are appropriately documented.

5.4.3 **Procedures for withdrawal from study**

Patients are at any time free to withdraw from the study (investigational product and assessments), without prejudice to further treatment (withdrawal of consent). Such patients will always be asked about the reason(s) and the presence of any adverse events. If possible, they will be seen by an investigator and undergo the assessments and procedures scheduled for the post study assessment (see Section 6.3.8) and inform AstraZeneca of the withdrawal. Adverse events should be followed up (see Sections 6.4.3 and 6.4.4); questionnaires (eg, for patient reported outcomes) and study drug should be returned by the patient.

5.5 Study timetable and end of study

Planned duration of the study:

Study period:

Dose escalation, paired biopsy and expansion cohorts

The primary analysis of the expansions will take place 7.5 months after the last patient recruited starts investigational product or approximately 28 days after the final patient discontinues investigational product. The initial CSR will report the analysis of all primary and secondary endpoints and summarise the exploratory endpoints where data is available. During the primary analysis of the extension cohort an updated analysis of DoR from one or more of the expansion cohorts may be performed.

Extension cohort

The primary analysis of ORR will take place after all patients have completed at least two RECIST follow-up assessments (i.e. 3months). At this time, DoR and safety/tolerability will also be summarised. The primary analysis CSR will report the analysis of ORR supported by duration of response, and safety and tolerability data.

The full CSR will report the analysis of all primary and secondary endpoints (including updated ORR and DoR, DCR, PFS, OS, HRQoL and PK). This analysis will take place approximately 8 months after the last subject has been enrolled into the extension cohort, to allow responding patients to have a DoR greater than 6 months.

All cohorts

All patients will continue to be followed up for an updated analysis that will occur between 12-24 months after the last patient has been enrolled. All endpoints will be updated and summarised in an addendum to the CSR.

Any patients still receiving investigational product at the time of the final data cut-off will be able to continue to receive AZD9291 while deriving clinical benefit. Such patients will continue to be monitored for all Serious Adverse Events up to 28 days after the last dose of investigational product. Drug Accountability information must still be collected until all patients have completed treatment.

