	Screening		ole Dose/(21 day cyc	-	Cycles 2-6 (21 day cycle)	Cycle 7 and every 6 weeks onwards	Discontin uation	28-day Follow up	Progress ion	Post progression survival F/U	Detail in section
Day	-28 to -1	D1	D8	D15	D1	D1				6 weekly relative to progression	
Tumour biopsy (optional)	X			Х			Х				6.8.1. 1
Vital signs	Х	X	Х	X	Х	Х	Х				6.3.3
Height	Х										6.3.3
Weight	X	Х			Х	Х	Х				6.3.3
Clinical chemistry /Haematology/Urinalysis	X	Х	X	Х	Х	Х	Х				6.3.5
ECG	Х	Х	Х	Х	Х	Х	Х				6.3.4
Echocadiogram/MUGA	Х	-	12 v	veekly rel	ative to first d	lose					6.3.7
PK blood sample (including metabolites)		Х	Х	Х	X (cycle 2 only)						6.6.1
Blood sample for cfDNA	Х	Х			6 wkly at RECIST visit X						6.8.1. 2
Genetic consent and blood sample (optional)	X										6.8.2
CSF (optional)		X (once only)								6.8.3	
RECIST assessments	Х	Every 6 weeks (relative to first dose) until progression)									6.10.1

Table 4Study Plan Phase II Extension Cohort

	Screening		ple Dose/C 21 day cyc	-	Cycles 2-6 (21 day cycle)	Cycle 7 and every 6 weeks onwards	Discontin uation	28-day Follow up	Progress ion	Post progression survival F/U	Detail in section
Day	-28 to -1	D1	D8	D15	D1	D1				6 weekly relative to progression	
Cognitive patient interview (optional)					4-0	6wks + 4-6 month	15				6.5.3
Dispense study medication		Х			Х	Х					5
Dose with AZD9291		-			Daily	v dosing					5
Concomitant medication	•										4.3.1
Adverse events											6.4
Survival										Х	6.3.8. 3

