6.10 Anti-tumour activity

6.10.1 Tumour assessments

RECIST 1.1 guidelines for measurable, non-measurable, target lesions (TLs) and non-target lesions (NTLs) and the objective tumour response criteria are presented in Appendix F of this Clinical Study Protocol.

Baseline CT or MRI assessments of chest and abdomen (including liver and adrenal glands) must be performed no more than 28 days before the start of study treatment, and ideally

should be performed as close as possible to the start of study treatment. Additional imaging may be performed based on individual patient signs and symptoms. CT/MRI scan of the brain should be performed in patients with known or suspected brain mestastases.

The methods of assessment used at baseline should be used at each subsequent follow-up assessment. Follow-up assessments should be performed every 6 weeks (\pm 7 days) after the start of multiple dosing until objective disease progression as defined by RECIST 1.1 even if a patient discontinues treatment prior to progression.

Any other sites at which new disease is suspected should also be appropriately imaged. If an unscheduled assessment is performed and the patient has not progressed, every attempt should be made to perform subsequent assessments at the scheduled visits whilst the patient remains on study treatment.

Categorisation of objective tumour response assessment will be based on the RECIST 1.1 guidelines for response: CR (complete response), PR (partial response), SD (stable disease) and PD (progression of disease). Target lesion progression will be calculated in comparison to when the tumour burden was at a minimum (i.e. smallest sum of diameters previously recorded on study). In the absence of progression, tumour response (CR, PR, SD) will be calculated in comparison to the baseline tumour measurements obtained before starting treatment.

If the investigator is in doubt as to whether progression has occurred, particularly with response to NTLs or the appearance of a new lesion, it is advisable to continue treatment and reassess the patient's status at the next scheduled assessment or sooner if clinically indicated. If repeated scans confirm progression, then the date of the initial scan should be declared as the date of progression.

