7.2.4 Phase II Extension Cohort

The primary endpoint of the extension phase is ORR. The extension will recruit approximately 175 patients with T790M mutation positive advanced NSCLC, whose disease has progressed following either one prior therapy with an EGFR-TKI (chemotherapy-naïve, n=50) or following treatment with both EGFR-TKI and other anti-cancer therapy (n=125). With 175 patients the precision of the estimation of ORR in the overall study population will be within +/-8% (e.g. ORR 40%, 95% CI 33.0%, 47.4%). The precision of the estimation of ORR will be within +/-13% in the 50 patient cohort who have only received previous TKI treatment and within +/-9% in the 125 patient cohort who have received previous TKI treatment and other anti-cancer therapy. The study will also provide an adequate number of patients in which to assess the safety and tolerability of AZD9291; if zero events are observed in the 175 patients, there is 95% confidence that the true event rate is less than 2.2%.

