For endpoints assessed by Independent Central Review, review of all radiological imaging data will be carried out using RECIST version 1.1. All radiological scans for all patients (including those at unscheduled visits, or outside visit windows), will be provided to the ICR. Prior radiotherapy and biopsied lesion reports for patients (at baseline) will also be provided to the ICR to allow the selection of appropriate target lesions. The imaging scans will be reviewed by two independent radiologists, using RECIST 1.1 criteria and will be adjudicated if required. For each patient, the ICR will define the overall visit response data (CR, PR, SD, PD or NE) and the relevent scan dates for each time point (i.e. for visits where response or progression is/is not identified).

7.7.1 **Objective response**

Objective response rate is defined as the percentage of patients who have at least one confirmed response of CR or PR prior to any evidence of progression (as defined by RECIST 1.1).

A visit response of CR is defined when all TL and NTL lesions present at baseline have disappeared (with the exception of lymph nodes which must be <10mm to be considered non-pathological) and no new lesions have developed since baseline. A visit response of PR is defined when the sum of diameters of the TLs has decreased by 30% or more compared to baseline (with no evidence of progression) and the NTLs are at least stable with no evidence of new lesions. A confirmed response of CR/PR means that a response of CR/PR is recorded at one visit and confirmed by repeat imaging at least 4 weeks later with no evidence of progression between confirmation visits.

In the case of stable disease, measurements should have met the stable disease criteria for a minumum interval of 5 weeks (6 weeks minus the 7-day visit window) following the start of treatment.

When the investigator is in doubt as to whether progression of disease has occurred and therefore reassesses the patient at a later date, the date of the initial scan should be declared as the date of progression if the repeat scans confirm progression.

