For the extension cohort, ORR rate is defined as the number (%) of subjects with measurable disease with at least one visit response of CR or PR that is confirmed at least 4 weeks later (according to ICR for the primary analysis). Data obtained up until progression, or last evaluable assessment in the absence of progression, will be included in the assessment of ORR. However, any complete response or partial response which occurred after a further anti-cancer therapy was received will not be included in numerator of the ORR calculation.

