For the expansion cohorts, the summaries will be by dose and centrally confirmed T790M status (positive, negative, unknown). First line cohort(s) will be summarised separately to pre-treated cohorts. A sensitivity analysis may be performed using local T790M status for patients whose central T790M status is not available.

For the extension cohort, all summaries will be presented as a cohort and by previous treatment cohort (TKI only or TKI plus additional treatments).. For the primary objective all RECIST outcomes will be based on the independent central review, and ORR will be summarised for the patients who have measurable disease at baseline as defined by ICR.

Tumour response data will be listed and summarised by dose group, and if appropriate using the following response categories: Complete Response (CR), Partial Response (PR), Stable Disease (SD), Progressive Disease (PD) and Non-Evaluable (NE).

Objective tumour response rates will be presented together with 80% and 95% confidence intervals (calculated using the Clopper-Pearson interval), where appropriate.

Duration of response

For the expansion and extension cohorts duration of response in responding patients will be summarised and the number (%) of responding patients with a duration of response >3; >6; >9; >12 months will be presented. A Kaplan Meier plot and median duration of response with 95% CI (calculated from the Kaplan Meier plot) will be presented. DCR will be summarised with 95% confidence intervals.

Progression free survival and overall survival

The analysis population for progression free survival and overall survival will be the safety population.

PFS will be summarised for the expansion phase and the extension phase. OS will be summarised for the extension phase only.

PFS and OS will be displayed using Kaplan Meier plots. The number of events, median (calculated from the Kaplan Meier plot), and proportion of patients without an event at 6, 12 and 18 months will be summarised.

As appropriate, summaries of the number and percentage of patients who have died, are still in survival follow-up, are lost to follow-up and have withdrawn consent will be presented.

Sensitivity analysis:

The same methods of analysis will be applied to analyse ORR, DoR, DCR, tumour shrinkage and PFS based on the RECIST data assessed by the Investigator

Change in tumour size

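### The extension cohort's primary ORR cut-off comes too early to confirm a response first seen at week 12 in the last-dosed patients, so the confirmed ORR is biased modestly downward

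*Protocol*

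**What the plan says.** Four rules in the protocol bear on the extension cohort's primary ORR.

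- **Cut-off (section 5.5):** "The primary analysis of ORR will take place after all patients have completed at least two RECIST follow-up assessments (i.e. 3months"). The same section plans an updated ORR in the full report about 8 months after the last enrolment, and a further update at 12 to 24 months.
- **Scan schedule (section 6.1, Table 4):** "Every 6 weeks (relative to first dose) until progression". Section 6.10.1 agrees ("Follow-up assessments should be performed every 6 weeks") and allows 7 days either side.
- **Numerator (section 7.7.1):** a patient counts with "at least one visit response of CR or PR that is confirmed at least 4 weeks later", by independent central review for the primary analysis. The general rule in the same section asks for a response "confirmed by repeat imaging at least 4 weeks later with no evidence of progression between confirmation visits".
- **Denominator (section 7.9):** "ORR will be summarised for the patients who have measurable disease at baseline as defined by ICR". Length of follow-up plays no part.

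No additional confirmatory scan is scheduled, and the protocol says nothing about responses still awaiting confirmation at the cut-off.

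**The concern.** A patient with only two follow-up scans has been imaged at about weeks 6 and 12. A response first seen at week 6 can be confirmed at week 12. A response first seen at week 12 has no later scan to confirm it, so it counts as a non-response only because the analysis came first.

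This matters because the extension exists to estimate ORR. Section 7.2.4 justifies its size by precision (within 8 percentage points either way) and states no hypothesis test. The binomial interval describes sampling error and does not allow for responses that are missing because of the cut-off. The size of the shortfall depends on how fast patients were enrolled near the end, which has nothing to do with the drug. ORR is also summarised by prior-treatment group (planned n=50 and n=125). If the two groups fill at different speeds, the shortfall differs between them.

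**Working it through.** **1. The plan's own figures.** Two scans at 6 weeks give 2 × 6 = 12 weeks, or 13 with the 7-day window. Three months is 3 × 30.4375 / 7 = 13.04 weeks. The stated cut-off therefore reproduces as week 12 to 13 for the last patient. The planning example in section 7.2.4 (ORR 40%, 95% CI 33.0% to 47.4%, n=175) also reproduces: 70/175 gives exactly that by the Wilson method. Clopper-Pearson gives 32.7% to 47.7%. The half-width is 7.2 to 7.5 points.

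**2. What can be confirmed by then.**

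- First response at week 6: the week-12 scan is nominally 6 weeks later. At the extremes of the window (week 7, then week 11) the gap is 4 weeks, which still qualifies.
- First response at week 12: 4 weeks later is week 16, or week 15 if the scan was done at week 11. Even an unscheduled scan would fall after the cut-off for the last patient. The next scheduled scan is week 18 (17 to 19).

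**3. Who is affected.** Patients with less than 18 weeks of follow-up at the cut-off, that is, those first dosed in the last 18 − c weeks of accrual, where c is the cut-off week for the last patient. With c = 12 or 13 this is the last 6 or 5 weeks.

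**4. Size.** With uniform accrual over A weeks and a share f of responders first responding at week 12:

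Loss in ORR = true ORR × f × (18 − c) / A

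A and f are not in the documents and are assumptions here. The 40% is the protocol's own planning example. With f = 0.18:

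| Accrual | Patients affected of 175 (c = 12 / 13) | Loss, c = 12 | Loss, c = 13 |
|---|---|---|---|
| 3 months (13 weeks) | 81 / 67 | 0.40 × 0.18 × 6/13 = 3.3 points | 0.40 × 0.18 × 5/13 = 2.8 points |
| 6 months (26 weeks) | 40 / 34 | 0.40 × 0.18 × 6/26 = 1.7 points | 0.40 × 0.18 × 5/26 = 1.4 points |
| 8 months (34.8 weeks) | 30 / 25 | 0.40 × 0.18 × 6/34.8 = 1.2 points | 0.40 × 0.18 × 5/34.8 = 1.0 point |

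**5. Range.** For f from 0.10 to 0.30 and accrual from 13 to 39 weeks:

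- Smallest loss: 0.40 × 0.10 × 5/39 = 0.5 points.
- Largest loss: 0.40 × 0.30 × 6/13 = 5.5 points.

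At a true ORR of 60% each loss is 1.5 times as large (0.8 to 8.3 points). Only the fastest-accrual, latest-response corner of that range exceeds the half-width.

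**6. After the fix.** With c = 18 the term (18 − c) is zero, so the loss from week-12 first responses disappears.

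**The case against.** The best case for the plan as written is that this is a small, conservative limitation of an early read-out that the protocol already follows up. Much of that stands.

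- **Two scans is a minimum.** Patients dosed earlier have a third scan, and week-6 responses are confirmable in everyone.
- **Large losses need fast accrual.** Enrolling 175 centrally tested T790M-positive patients in 3 months is optimistic. Slower accrual brings the loss to about 1 point under the central assumption.
- **No decision rule is affected.** The protocol gives no null rate or go/no-go threshold for this ORR.
- **A later ORR is planned.** At about 8 months (34.8 weeks) after the last enrolment, a response first seen at week 12 or week 18 has passed its confirming scan time in every patient.

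These points limit the size and the consequence. They do not remove the error: in an estimation cohort, a conservative bias still affects the quantity being estimated, and section 5.5 makes the 3-month figure the primary one.

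A reader might infer two stronger things. The first is that a true 40% would read about 34%. With fast 3-month accrual, a week-12 cut and 7% of responders first responding at week 18, the total loss is indeed 3.3 + 0.40 × 0.07 × 12/13 = 3.3 + 2.6 = 5.9 points. But the 2.6 points are ordinary truncation of later responses, not the mismatch described here. A third-scan cut-off would still leave 0.40 × 0.07 × 6/13 = 1.3 points of them. The second is that the updated ORR will contradict the primary result. A planned update that rises by a few points as pending scans arrive is not a contradiction.

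**Conclusion.** The point holds, at modest size. The cut-off, scan interval, confirmation rule and denominator are all fixed in the protocol. Together they make a first response at week 12 count as a non-response in patients dosed in about the last 5 to 6 weeks of accrual. The direction is certain: downward.

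The size rests on assumptions that the documents do not supply. With uniform accrual over 3 to 8 months, a true ORR of 40% and 18% of responders first responding at week 12, the loss is about 1 to 3 percentage points. It is 0.5 to 5.5 points for accrual of 3 to 9 months and a share of 10% to 30%. In most scenarios this is below the planned half-width of 7 to 8 points. The 8-month update should largely correct the estimate, so what remains is that the primary-analysis report would present the lower figure as the primary result. The documents do not support reading this as a threat to the cohort's conclusions. It should be corrected because correction is cheap.

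**What to change.** Amend section 5.5 in one of two ways.

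1. Set the extension cohort's primary ORR cut-off at the point when every patient has had the opportunity for three RECIST follow-up assessments (week 18 plus 7 days after the last patient's first dose). This moves the cut-off from about week 13 to week 19, a delay of about 6 weeks. It needs no new scans or patients, because the week-18 scan is already scheduled.
2. Keep the 3-month look, label it interim, and name the ORR at a later cut as primary. The already planned 8-month analysis would serve. The early read-out is not delayed, but if that analysis is used, the result carrying the primary label arrives about 5 months later than now (8 − 3).

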7.7.2 Progression Free Survival

PFS is defined as the time from date of first dosing until the date of objective disease progression as defined by RECIST 1.1 or death (by any cause in the absence of progression) regardless of whether the subject withdraws from AZD9291 therapy or receives another anti-cancer therapy prior to progression.

Patients who have not progressed or died at the time of analysis will be censored at the time of the latest date of assessment from their last evaluable RECIST assessment. If the patient has no evaluable visits or does not have baseline data they will be censored at 0 days unless they die within two visits of baseline.

If a patient discontinues treatment prior to progression and/or receives a subsequent therapy prior to progression then these patients will continue to be followed until evidence of objective disease progression as defined by RECIST 1.1 and their PFS time will be derived as defined above.

Note: Symptomatic deterioration will not be regarded as a progression event.

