7.7.3 Duration of Response

Duration of response will be defined as the time from the date of first documented response, (that is subsequently confirmed (as defined in Section 7.7.2)) until date of documented progression or death in the absence of disease progression, the end of response should coincide with the date of progression or death from any cause used for the PFS endpoint. The time of the initial response will be defined as the latest of the dates contributing towards the first visit response of PR or CR.

If a subject does not progress following a response, then their duration of response will use the PFS censoring time.

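### The full-CSR timing rationale overlooks scan-based censoring for the last-enrolled responders, and the planned DoR landmark percentages count responders censored before a landmark as not reaching it

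*Protocol*

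**What the plan says.** Section 5.5 (Extension cohort) gives both the timing of the full report and its purpose. It is to take place about "8 months after the last subject has been enrolled into the extension cohort, to allow responding patients to have a DoR greater than 6 months"; the protocol words the time as approximate. The same section plans an update of all endpoints 12 to 24 months after the last enrolment.

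Four other rules decide what duration of response (DoR) can be recorded by then:

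- Section 6.10.1: "Follow-up assessments should be performed every 6 weeks", with 7 days allowed either side. Table 4 times the extension cohort's scans from first dose.
- Section 7.7.3: DoR starts at the first response that is later confirmed. For ongoing responses, "If a subject does not progress following a response, then their duration of response will use the PFS censoring time".
- Section 7.7.2: that time is "censored at the time of the latest date of assessment from their last evaluable RECIST assessment", not the data cut-off date.
- Section 7.9, for the expansion and extension cohorts: "the number (%) of responding patients with a duration of response >3; >6; >9; >12 months will be presented". A Kaplan-Meier curve and a median with its 95% interval are also planned. Kaplan-Meier estimates at the four landmarks are not mentioned.

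**The concern.** The two parts of the point share a cause: administrative censoring at the last scan.

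First, the 8-month figure appears to subtract the time to first response from calendar follow-up. The protocol's own rule stops the clock at the last scan, which can fall several weeks before the cut-off. For the patients enrolled last, the stated purpose may then not be met.

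Second, if DoR equals the censoring time for an ongoing responder, someone censored at 5.5 months does not have a DoR above 6 months but remains in the denominator. The percentage then mixes true loss of response with short follow-up.

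In a single-arm cohort whose primary endpoint is the response rate, DoR is the main supporting evidence. A landmark percentage that is low only because follow-up is short would sit beside a Kaplan-Meier curve that says something different.

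**Working it through.** **Inputs from the protocol.** Cut-off about 8 months after last enrolment and target DoR above 6 months (5.5). Scans at weeks 6, 12, 18, 24, 30 and 36, ±7 days (6.10.1, Table 4). DoR start and censoring rules (7.7.2, 7.7.3). One month is taken as 365.25/12 = 30.4375 days.

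**The protocol's figure, reproduced in calendar time.** 8 months − 42/30.4375 months = 8 − 1.38 = 6.62 months. This exceeds 6 and is probably the reasoning behind the sentence.

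**The same figure under the censoring rule**, for a patient enrolled last and dosed the same day:

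- 8 × 30.4375 = 243.5 days = 34.8 weeks, so the last scheduled scan is week 30 (day 210).
- First response at week 6: 210 − 42 = 168 days = 5.5 months.
- First response at week 12: 210 − 84 = 126 days = 4.1 months.
- Window extremes (week-6 scan on day 35, week-30 scan on day 217): 217 − 35 = 182 days = 5.98 months, against 6 × 30.4375 = 182.6 days.
- Earliest in-window week-36 scan: 252 − 7 = day 245, which is 1.5 days after day 243.5.
- A 28-day gap between enrolment and first dose leaves 30.8 weeks of follow-up. The last nominal scan is still week 30, so the result is unchanged.

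**How many responders this touches.** Accrual time and response timing are not in the protocol. Assume uniform accrual over 6 months (182.6 days) and no gap before first dose. The share enrolled too late to be scanned beyond 6 months of response is:

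- week-6 responders: (252 − 243.5)/182.6 = 5%
- week-12 responders: (294 − 243.5)/182.6 = 28%
- week-18 responders: (336 − 243.5)/182.6 = 51%

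With first responses split 80/20 over weeks 6 and 12, this is 0.80 × 4.7 + 0.20 × 27.7 = 9% of responders. With a 75/18/7 split over weeks 6, 12 and 18, it is 0.75 × 4.7 + 0.18 × 27.7 + 0.07 × 50.7 = 12%.

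**Landmark percentages at the 8-month cut-off.** Simulation of 40,000 responders per scenario, with the 80/20 split, exponential DoR, progression recorded at the next scan and censoring at the last scan before the cut-off. Each range runs from a median DoR of 9 months to one of 12 months. All of these are assumptions.

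| Accrual | Landmark | Observed n/N | Kaplan-Meier |
|---|---|---|---|
| 3 months | >6 months | 53–59% | 65–73% |
| 6 months | >6 months | 60–66% | 66–72% |
| 6 months | >9 months | 24–28% | 53–61% |
| 6 months | >12 months | 1–2% | 43–53% |
| 9 months | >6 months | 61–68% | 65–73% |
| 9 months | >9 months | 33–39% | 53–62% |
| 9 months | >12 months | 14–17% | 43–53% |

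With 3-month accrual, even the first patient has 11 months of follow-up (334.8 days). The last scan is then day 294 and the longest DoR 294 − 42 = 252 days (8.3 months). The observed figure above 9 months is therefore 0% whatever the true durability, and no estimate should be shown there.

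**At the later update.** With a cut-off 12 months after last enrolment and 6-month accrual, the >6-month gap disappears and the >9-month gap is about 1 point. The >12-month gap remains: 28–34% observed against 43–53%.

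**The case against.** The case on the other side has force on several points.

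- **Approximate timing.** The protocol says approximately 8 months, and the earliest week-36 scan misses by 1.5 days. Eight calendar months span 242 to 245 days, and counting both end dates turns 182 days into 183. This stands for edge cases, but it does not help a responder scanned on schedule.
- **No promise to every responder.** A reader might infer that no responder can exceed 6 months at this cut-off. The protocol does not support that: patients enrolled earlier can, and in the scenarios above more than half of responders do. Nor is 5.5 months a ceiling for the last-enrolled. Window extremes give 182 days, a death after week 30 can end a longer DoR, and unscheduled scans also go to central review (Section 7.7).
- **Not all censored responders are miscounted.** A reader might infer that every ongoing response is treated as a failure. A responder censored after a landmark is correctly counted as exceeding it, so only those censored before it are affected.
- **Kaplan-Meier is already planned, and an SAP not shown could add landmark rates.** The curve and median do handle censoring, so the DoR analysis as a whole is not invalid. But the protocol itself states both the n (%) summary and the rule giving a censored responder a DoR equal to the censoring time. Followed as written, they give the biased figure, so this is not just detail left to an SAP.
- **The largest gaps are at 9 and 12 months, which the 8-month sentence does not address.** Correct. They belong to the landmark summary, and a modestly later cut-off would not remove them.

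**Conclusion.** Both parts hold within limits. For a last-enrolled, on-schedule responder, the 8-month timing gives a scan-based DoR of 5.5 months (first response at week 6) or 4.1 months (week 12). This follows from the protocol alone. It is a narrow miss confined to late enrollees: roughly 9 to 12% of responders under 6-month accrual and the assumed response timings.

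The landmark percentages have the wider effect. They are biased downward whenever a responder is censored before the landmark. The direction follows from the text, but the size depends on accrual and true DoR, which the protocol does not give. In the scenarios shown, the shortfall is about 4 to 14 percentage points at 6 months and much larger at 9 and 12 months.

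The response rate, the DoR definition and the planned Kaplan-Meier curve and median are unaffected. The later update removes the 6-month problem, but only after the full report has been issued.

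**What to change.** 1. In Section 7.9, report Kaplan-Meier estimates of the proportion still in response at 3, 6, 9 and 12 months, with 95% confidence intervals and numbers at risk, in place of or alongside the counts. If counts stay, label them as observed and show how many responders were censored before each landmark. Numbers at risk matter because few responders will have been followed to the later landmarks. This needs no new data, since the Kaplan-Meier analysis is already planned.

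2. In Section 5.5, choose one of two changes:
   - Define the cut-off from first dose, so that all patients have passed the week-36 scan window: 252 + 7 = 259 days, about 8.5 months. A week-6 responder can then show 252 − 42 = 210 days (6.9 months). The cost is 259 − 243.5 = 15.5 days, about two weeks, plus any gap between the last patient's enrolment and first dose (screening allows up to 28 days). Week-12 responders enrolled last would still reach only 252 − 84 = 168 days (5.5 months). Covering them needs the week-42 window (294 + 7 = 301 days, 9.9 months), a longer delay that is a trade-off for the sponsor and is not required here.
   - Keep approximately 8 months and reword the rationale to say that the last-enrolled responders will generally have scan-based follow-up of response of just under 6 months. The cost is one sentence.
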